6.7.2 Secondary Efficacy Analysis

The first secondary endpoint, the proportion of treatment targeted BCCs with Complete or Partial Response as determined by blinded photographic review will be evaluated using a 2-sided Fisher's Exact test. This analysis will be performed on all available data with no imputation of missing data. Both pairwise comparisons between treatment groups and all treated (combining all patidegib groups) versus vehicle will be done.

The second secondary endpoint, the greatest diameter of all treatment targeted BCCs, will be evaluated similarly to the primary endpoint. This analysis will be performed using LOCF imputation as well as 'as observed' (i.e. no imputation of missing data).

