6.3 Subject Withdrawal Criteria

Participation in the study is strictly voluntary. A subject has the right to withdraw from the study at any time for any reason and is under no obligation to disclose the reason. If a subject withdraws, the Investigator is to be informed immediately.

The Investigator has the right to terminate participation of a subject at any time for any of the following:

- Intake or use of non-permitted concomitant medication
- Lack of subject compliance
- Protocol violation Contact PellePharm or designee before making decision.
- Disease progression The Investigator and/or PSCP believe that delaying the treatment of the treatment targeted tumor until the end of the trial would cause harm to the subject.
- Worsening of any condition Subject requires alternate treatment before the end of the study and the Investigator determines it is not due to lack of efficacy.
- A perceived safety risk
- Adverse Event Complete AE form
- Lost to Follow-Up Document with at least 2 phone calls and a certified letter
- Subject Request Consent withdrawal, subject moved, schedule conflicts
- Pregnancy If subject or subject's sexual partner become pregnant the subject will discontinue study drug immediately, but the pregnancy will be followed until delivery. Complete pregnancy form
- Lack of Efficacy Subject requires alternate treatment after at least 2 weeks of study drug treatment and the Investigator determines that the risk of continuing the subject in the study outweighs the benefit. However, if a subject has two treatment-targeted BCCs and one of the BCCs requires treatment because of an increase in size, the tumor can be treated and the subject can remain in the trial.
- Other Specify in comments section of electronic case report form (eCRF)

If a study subject experiences disease progression or begins another treatment for his/her disease, follow-up per protocol will no longer be required.

Subjects who terminate treatment early will be asked to complete all Week 12 assessments prior to commencement of any alternative therapy (if possible). Subjects who discontinue from the study during the treatment period will not be replaced.

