5.1.2 Secondary Efficacy Endpoint

The secondary efficacy endpoint is the decrease in tumor size defined in two ways:

1. Percent of baseline treatment targeted BCCs with Complete or Partial Response at Week 12 as assessed by blinded photographic review where Complete Response is determined when there is no longer any visible evidence of a lesion consistent with BCC at the site, Partial Response is determined when although a BCC still remains at this site, it has demonstrated a visible decrease in size compared with baseline, and No Response is

determined when the BCC has not demonstrated any visible decrease in size compared with baseline, and;

2. Percent decrease in the greatest diameter of baseline treatment targeted BCCs at Week 12.

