6. STATISTICAL AND ANALYTICAL PLANS

6.1 General Methodology

All statistical processing will be performed using Statistical Analysis System (SAS®) unless otherwise stated. No interim analyses are planned. If determined appropriate by the Sponsor, limited safety and efficacy interim analysis on tumor shrinkage and biomarkers may be performed.

Formal inferential testing will not be performed, however p-values will be provided for descriptive purposes. Descriptive statistics will be used to provide an overview of the efficacy and safety results. P-values which are supplied are for descriptive purposes only. For categorical parameters, the number and percentage of subjects in each category will be presented. For continuous parameters, descriptive statistics will include n (number of subjects), mean, standard deviation (SD), median, minimum (min), and maximum (max). For by treatment group summaries the vehicle gel group from each cohort will be combined into a single group.

The last observation carried forward method (LOCF) will be used to impute missing secondary and exploratory efficacy data (i.e., the last available on-therapy observation for a subject will be used to estimate subsequent missing data points). Analyses will also be carried out on an 'as

observed' basis without imputation. No imputations will be made for missing primary endpoint data or safety data.

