6.1.5 Handling of Dropouts or Missing Data

If a partial date is recorded for an adverse event start or end date, the following procedure will be followed. Other missing safety data dates will not be imputed.

If a partial date is reported where the day is missing, then the day will be imputed as the first day of the month unless the month is the same month as the first dose in which case the day will be that of first dose with the month and year remaining the same. If a partial date is reported where the month is missing, then the month will be imputed to January unless the year is the same year as the first dose in which case the month will be that of first dose with the year remaining the same. If a partial date where both the day and month is missing, follow details as stated previously.

Missing data post-Baseline through Week 12 will be imputed using last observation carried forward (LOCF) for the secondary endpoint of tumor size as assessed by the investigator. Specifically, if a single diameter is missing then that SEB's previous measurement will be carried forward. The analysis will also be performed without imputation of missing data. For the secondary endpoint of GLI1, no missing data will be imputed.

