Min. to Max.	xx to xx	xx to xx	xx to xx	xx to xx	xx to xx
At least 40% Decrease from Baseline	xx (xx.x%)	xx (xx.x%)	xx (xx.x%)	xx (xx.x%)	xx (xx.x%)

P-value versus Vehicle Gel ^b	X.XXX	X.XXX	X.XXX	X.XXX	
P-value versus Patidegib Gel 2% QD ^b		X.XXX	X.XXX	X.XXX	
P-value versus Patidegib Gel 2% BID ^b			X.XXX	X.XXX	
P-value versus Patidegib Gel 4% QD ^b				X.XXX	
P-value All Patidegib vs Vehicle Gel					X.XXX
P-value versus Vehicle Gel ^c	X.XXX	X.XXX	X.XXX	X,XXX	
P-value versus Patidegib Gel 2% QD ^c		X.XXX	X.XXX	X.XXX	
P-value versus Patidegib Gel 2% BID ^c			X.XXX	X,XXX	
P-value versus Patidegib Gel 4% QD ^c				X.XXX	
P-value All Patidegib vs Vehicle Gel					X.XXX

Repeat Above for 1:BCC + tumor-associated stroma region H-Score

Note: Missing values are not imputed; all available data is summarized.

SOURCE: USERNAME\SPONSOR\PROJECT\JOBNAME (DATE,TIME)

^a Change from Baseline calculated as (Week 12 – Baseline). Percent Change from Baseline calculated as (Week 12 - Baseline) / Baseline * 100. ^b P-value of pairwise comparison using ANCOVA with a factor of treatment group and using Baseline value as a covariate.

^c P-value of pairwise comparison using t-test (or Mann Whitney U if the case).

Table 14.2.2.1.1: Analysis of the Secondary Efficacy Endpoint: Proportion of CR/PR Response at Week 12 (Intent-to-Treat Population)

	Patidegib Gel 2% QD (N=xx)	Patidegib Gel 2% BID (N=xx)	Patidegib Gel 4% QD (N=xx)	Patidegib Gel 4% BID (N=xx)	Vehicle Gel (N=xx)
Proportion of CR/PR Response at					
Week 12 ^a					
Number of tumors	XX	XX	XX	XX	XX
CR / PR	XX.X	XX.X	XX.X	XX.X	XX.X
Non Response	XX.XX	XX.XX	XX.XX	XX.XX	XX.XX
P-value versus Vehicle Gel ^c	x.xxx	x.xxx	x.xxx	X.XXX	
P-value versus Patidegib Gel 2% QD ^c		X.XXX	X.XXX	X.XXX	
P-value versus Patidegib Gel 2% BID ^c			X.XXX	X.XXX	
P-value versus Patidegib Gel 4% QD ^c				X.XXX	
P-value All Patidegib vs Vehicle Gel					x.xxx

Note: Missing values are not imputed.

SOURCE: USERNAME\SPONSOR\PROJECT\JOBNAME (DATE,TIME)

Table 14.2.2.1.2: Analysis of the Secondary Efficacy Endpoint: Proportion of CR/PR Response at Week 12 (Per Protocol Population)

As assessed by blinded photographic review.
 P-value of pairwise comparison using 2-sided Fisher's Exact test.

Table 14.2.2.2.1: Analysis of the Secondary Efficacy Endpoint: Percent Decrease in Baseline Treatment Targeted Tumor Size at Week 12 (LOCF) (Intent-to-Treat Population)

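### The CR/PR analysis uses available Week 12 ratings only, so tumors that fail and exit early leave the ITT denominator instead of counting as non-response

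*SAP*

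**What the plan says.** SAP 5.1.2 makes CR/PR at Week 12, by blinded photographic review, the first of two secondary endpoints. SAP 6.7.2 compares it by two-sided Fisher's exact test, between groups and for all patidegib against vehicle. On missing ratings it says: "This analysis will be performed on all available data with no imputation of missing data". The shell for Table 14.2.2.1.1, the ITT version, repeats this: "Note: Missing values are not imputed".

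The category definitions in SAP 5.1.2 assume a rated photograph. No Response is "determined when the BCC has not demonstrated any visible decrease in size compared with baseline". Complete Response applies when "there is no longer any visible evidence of a lesion consistent with BCC at the site". Neither definition mentions a tumor with no rating or one treated by other means.

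Protocol 6.3 allows withdrawal for disease progression and for lack of efficacy, and adds: "If a study subject experiences disease progression or begins another treatment for his/her disease, follow-up per protocol will no longer be required". It also allows one of two target tumors to be treated because it has grown, with the subject staying in the trial. Protocol 6.3 and Table 1 (footnote a) ask for the Week 12 evaluations at early termination, and Table 1 schedules imaging at that visit.

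SAP 6.1.3 assigns early-termination data to visits by study day, with days 82 to 88 for Week 12. Data that map to no window are not analyzed.

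On imputation, SAP 6.1 states generally: "The last observation carried forward method (LOCF) will be used to impute missing secondary and exploratory efficacy data". SAP 6.1.5 is narrower and applies LOCF "for the secondary endpoint of tumor size as assessed by the investigator".

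**The concern.** A tumor can lack a Week 12 rating because treatment did not work. Removing it from numerator and denominator alike turns the rate into one among tumors that did well enough to be followed to Week 12, while the table is presented as ITT.

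The trial's stated goal in the Introduction is to establish a dose and regimen for later trials. Each regimen has 6 subjects, so one or two such removals can change how a regimen looks beside the others and beside vehicle.

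**Working it through.** **No plan figure to reproduce.** Neither document gives a response rate, dropout rate, power or sample-size calculation. SAP section 7 says only that the study is dose ranging. The design arithmetic is 4 × (6 + 3) = 36 subjects: 24 patidegib and, with vehicle pooled under SAP 6.1, 12 vehicle. At one or two tumors each, that is 24 to 48 patidegib and 12 to 24 vehicle tumors.

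**Step 1: does an exit photograph count as Week 12?** The SAP 6.1.3 windows before Week 12 are days 13–17 (5 days), 40–46 (7), 54–60 (7) and 68–74 (7).

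- Exit days 1–81 that map to Week 12: 0.
- Exit days that map to an earlier visit: 5 + 7 + 7 + 7 = 26.
- Exit days in no window: 81 − 26 = 55.

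Only an exit on days 82–88 supplies a Week 12 rating. Otherwise SAP 6.7.2 leaves the tumor out.

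**Step 2: effect on the rate and the difference.** Suppose an arm has true response rate p and loses a share f of its tumors, all non-responders. The available-data rate is p/(1 − f), which exceeds p by p·f/(1 − f). The bias in the difference is therefore

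p_A·f_A/(1 − f_A) − p_V·f_V/(1 − f_V),

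where A is patidegib and V is vehicle. With equal shares f it equals (p_A − p_V)·f/(1 − f), which exaggerates whatever difference exists.

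**Step 3: pooled illustration.** Assumptions: one tumor per subject, true results 16/24 and 4/12, every lost tumor a non-responder. P-values are two-sided Fisher's exact.

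| Lost (active, vehicle) | Active | Vehicle | Difference | p |
|---|---|---|---|---|
| Failures counted | 16/24 = 66.7% | 4/12 = 33.3% | 33 points | 0.081 |
| 2, 3 | 16/22 = 72.7% | 4/9 = 44.4% | 28 points | 0.22 |
| 2, 1 | 16/22 = 72.7% | 4/11 = 36.4% | 36 points | 0.065 |
| 4, 0 | 16/20 = 80.0% | 4/12 = 33.3% | 47 points | 0.021 |

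The row with 2 and 1 lost is an equal 8.3% loss (2/24 and 1/12), and it favors the drug. At these rates p_A is twice p_V, so the bias runs against the drug only if f_V/(1 − f_V) is more than twice f_A/(1 − f_A). With 2 and 3 lost these are 3/9 = 0.33 and 2/22 = 0.09, so it does.

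**Step 4: one regimen.** Assume 3/6 on a regimen against 3/12 on vehicle, which is 50% versus 25% (p = 0.344). Losing 1, 2 or 3 failed patidegib tumors moves the regimen to 3/5 = 60%, 3/4 = 75% or 3/3 = 100% (p = 0.280, 0.118, 0.044). With failures counted it stays at 50%.

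**Step 5: a tumor treated by other means.** If its site is photographed at Week 12 and no lesion is visible, the SAP 5.1.2 wording permits a Complete Response. One such tumor in a regimen with 3/6 responders gives 4/6 = 67% instead of 50%.

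**The case against.** **Exit photographs are planned.** A reader of the follow-up sentence in Protocol 6.3 might infer that failed tumors go unphotographed. The same section and Table 1 do not support that, because they ask for the Week 12 evaluations, including imaging, at early termination. This stands: the loss comes largely from the visit windows in SAP 6.1.3, and an exit on days 82–88 is kept.

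**Direction.** A reader might infer that the rule usually works against the drug because vehicle should fail more often. No loss figures by arm are given, and equal losses push the other way (Step 3).

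**Size.** Losses may be few. Section 4 of the protocol describes slow growth: a median increase of 0.5 mm over a mean of 70 days in untreated sporadic tumors. That makes a 25% vehicle loss to failure look high, and the counts above are illustrations only. It does not remove the sensitivity of a group of 6.

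**Consequences.** P-values are descriptive, and this is one of two secondary endpoints. The tables show the number of tumors rated and the reasons for discontinuation by arm, so a shrinking denominator can be seen. One might say the ITT label fails; SAP 6.4.1 defines ITT by who was randomized and dispensed drug and by analysis as randomized, so that is too strong. The defect is in the handling of missing ratings.

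**LOCF.** SAP 6.1 read alone suggests that a missing CR/PR rating is carried forward. SAP 6.1.5, SAP 6.7.2 and the table note agree that it is not, so this is an alignment point. Neither rule counts a lost tumor as non-response.

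**Conclusion.** The concern holds in this form. As written, a failed target tumor whose subject exits before day 82 is not in the ITT CR/PR rate, and a tumor treated by other means could be rated a responder. The rate is inflated in any arm that loses failed tumors. In the pooled illustration the difference ranges from 28 to 47 points against 33 with failures counted; a single regimen of 6 can move from 50% to 60% with one loss. These sizes rest on assumed response counts, assumed losses, one tumor per subject, and every lost tumor being a non-responder.

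The documents do not support a claim about which way the contrast with vehicle is biased. No formal error rate is at stake. What is affected is the estimated response rates and, through them, the choice of regimen. The rule should be changed before the CR/PR data are analyzed.

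**What to change.** In SAP 6.7.2, for the ITT analysis:

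- Count as No Response any target tumor with no Week 12 photographic rating, and any target tumor treated by other means before its Week 12 rating.
- Keep the available-data analysis as a sensitivity analysis.
- Report the number of unrated tumors by arm, with reasons.

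In SAP 6.1, state that LOCF does not apply to CR/PR, and change the note to Table 14.2.2.1.1 to match.

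The cost is SAP wording and one extra table; no new data are needed. The drawback is that losses unrelated to efficacy, such as loss to follow-up, adverse events or an unusable photograph, also count as non-response. Rates become slightly less favourable, and an arm with more such exits is marked down for them. The sensitivity analysis and the reasons by arm show how much of the result depends on this.

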6.7.3 Exploratory Efficacy Analysis

The exploratory endpoint of investigator static global tumor assessment (ISGTA) will be summarized by visit on a by tumor level. Proportion with success as defined by Clear/Almost Clear will be provided. Results will be analyzed with a Cochran-Mantel-Haenszel (CMH) test.

Tumor area will be evaluated with an analysis of covariance (ANCOVA) with treatment group as factor and baseline value as covariate. Analysis is on a by tumor level. Pairwise comparisons as well as any treated (combining all patidegib groups) versus vehicle will be performed using contrasts within the ANCOVA.

The proportion of baseline treated tumors are smaller at each study visit based on photographic review will be summarized by treatment group. Results will be analyzed between groups and all treated (combining all patidegib groups) versus vehicle with a CMH test. Tumor area will be summarized by visit.

6.8 Safety Evaluation

6.8.1 Extent of Exposure and Compliance

The extent of exposure to study drug in each treatment group will be summarized by days with applications, total number of applications, and number of missed applications. This data will also be provided in a listing.

Percent compliance will be calculated for each subject as follows:

(a) Expected Number of Applications = (Date of Last Application – Date of First Application + 1) * Number of Expected Applications per day, accounting for possible single applications on First and/or Last Day

(b) Total Number of Applications = Expected Number of Applications – Total Number of Missed Applications

Compliance = (b) / (a) * 100

6.8.2 Adverse Events

All AEs that occur during the study will be recorded and classified on the basis of Medical Dictionary for Regulatory Activities (MedDRA) terminology. Treatment-emergent Aes (TEAEs) are defined as Aes with an onset on or after the date of the first study drug application. Adverse events noted prior to the first study drug administration that worsen after Baseline will also be reported as Aes and included in the summaries.

Treatment-emergent Aes will be summarized by treatment group, the number of subjects reporting a TEAE, SOC, preferred term, severity, relationship to study drug (causality), and seriousness. When summarizing Aes by severity and relationship, each subject will be counted once within a system organ class or a preferred term by using the event with the highest severity and greatest relationship within each classification.

If relationship to study drug is reported as unknown, possible, probable or definite, then this is defined as related. If relationship to study drug is reported as unlikely or not related, then this is defined as unrelated.

Serious Aes will be summarized by treatment group, severity and relationship to study drug.

Listings will be presented for all adverse events as well as for serious adverse events and adverse events leading to study drug withdrawal.

6.8.3 Clinical Laboratory Evaluation

Laboratory test results will be summarized with descriptive statistics at Baseline and Week 12. Additionally, shifts from Baseline to Week 12 in laboratory test results based on normal ranges will be summarized with frequency counts and percentages. Individual laboratory test results will be presented in a by-subject listing.

6.8.4 Other Observations Related to Safety

6.8.4.1 Dermal Safety and Tolerability

The frequency of dermal safety and tolerability assessments including pain/burning, pruritus, erythema, edema, and scabbing/crusting will be summarized by treatment group and visit. All dermal safety and tolerability results will be listed.

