10.8.3 Safety Laboratory Values and Vital Sign Measurements

Changes from Baseline in safety laboratory values and vital sign measurements will be summarized with descriptive statistics for each treatment group at all applicable study visits.

Shift tables will be presented for changes in safety laboratory values to summarize laboratory test results collected at Screening and Weeks 6, and 12. Normal ranges established by the local laboratory will be used to determine the shifts. A listing of all out-of-range laboratory test results at any assessment time point will also be provided. Determination of clinical significance for all out-of-range laboratory values will be made by each Investigator and included in the listing. In addition, a listing of all clinically significant laboratory test results will be provided.

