3. STUDY OBJECTIVES

The primary objectives of the study are to evaluate the following:

- 1. The safety and tolerability of treatment with patidegib gel 2% or 4% or vehicle applied once or twice daily for 12 weeks.
- 2. The molecular efficacy of treatment as defined by reduction in the hedgehog (HH) signaling pathway after treatment with patidegib gel 2% or 4% or vehicle applied twice daily for 12 weeks to treatment-targeted BCCs.

The secondary objective of the study is to evaluate the following:

1. The clinical efficacy of patidegib as defined by the percent decrease in greatest diameter of baseline treatment targeted basal cell carcinomas after 12 weeks of treatment. Treatment targeted BCCs will be biopsied prior to treatment to confirm the clinical diagnosis of nodular BCC. Eligible tumors will have the clinical features of nodular BCC and prior to biopsy will be no less than 5 mm or greater than 20 mm in longest diameter on the face (excluding the nose and periorbital skin) and no less than 9 mm or greater than 20 mm in longest diameter at sites other than the face.

Exploratory objectives:

- 1. To evaluate the utility of an investigator static global tumor assessment (ISGTA) in assessing the proportion of baseline treatment-targeted BCCs that are evaluated as being clear or almost clear.
- 2. To evaluate the utility of blinded assessment of change in BCC size using photographs.

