6.8.4.2 Systemic Symptoms

Systemic symptoms will be summarized by treatment group and visit. Additionally, results will be listed.

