Table	14.2.4.4: Analysis of the Ex	xploratory Efficacy Endpo	int: Area of Baseline Trea	nted Tumors based on Pho	otographic Review (Per Pr	rotocol Population)
Analysis Pla	n for PellePharm, Inc.			Page 40		
umber: 926-	202			Page 40 28Sep2017		

Table 14.3.1.2.1: Summary of Dermal Safety and Tolerability (Safety Population)
(Page 1 of x)

Pain / Burning	Patidegib Gel 2% QD (N=xx)	Patidegib Gel 2% BID (N=xx)	Patidegib Gel 4% QD (N=xx)	Patidegib Gel 4% BID (N=xx)	Vehicle Gel (N=xx)
Baseline					
Number of tumors	XX	XX	XX	XX	XX
None	xx (xx.x%)	xx (xx.x%)	xx (xx.x%)	xx (xx.x%)	xx (xx.x%)
Mild	xx (xx.x%)	xx (xx.x%)	xx (xx.x%)	xx (xx.x%)	xx (xx.x%)
Moderate	xx (xx.x%)	xx (xx.x%)	xx (xx.x%)	xx (xx.x%)	xx (xx.x%)
Severe	xx (xx.x%)	xx (xx.x%)	xx (xx.x%)	xx (xx.x%)	xx (xx.x%)
Week 2					
Number of tumors	XX	XX	XX	XX	XX
None	xx (xx.x%)	xx (xx.x%)	xx (xx.x%)	xx (xx.x%)	xx (xx.x%)
Mild	xx (xx.x%)	xx (xx.x%)	xx (xx.x%)	xx (xx.x%)	xx (xx.x%)
Moderate	xx (xx.x%)	xx (xx.x%)	xx (xx.x%)	xx (xx.x%)	xx (xx.x%)
Severe	xx (xx.x%)	xx (xx.x%)	xx (xx.x%)	xx (xx.x%)	xx (xx.x%)

Continue for Weeks 6, 8, 10, 12

Repeat for Pruritus, Erythema, Edema, Scabbing / Crusting

Note: Local safety and tolerability is reported by the subject as the greatest intensity since the last visit or within 24 hours at Baseline.

Table 14.3.1.2.2: Summary of Systemic Symptoms (Safety Population) (Page 1 of x)

Fatigue Baseline	Patidegib Gel 2% QD (N=xx)	Patidegib Gel 2% BID (N=xx)	Patidegib Gel 4% QD (N=xx)	Patidegib Gel 4% BID (N=xx)	Vehicle Gel (N=xx)
n	xx	XX	XX	XX	XX
Yes	xx (xx.x%)	xx (xx.x%)	xx (xx.x%)	xx (xx.x%)	xx (xx.x%)
No	xx (xx.x%)	xx (xx.x%)	xx (xx.x%)	xx (xx.x%)	xx (xx.x%)
Week 2					
n	XX	XX	XX	XX	XX
Yes	xx (xx.x%)	xx (xx.x%)	xx (xx.x%)	xx (xx.x%)	xx (xx.x%)
No	xx (xx.x%)	xx (xx.x%)	xx (xx.x%)	xx (xx.x%)	xx (xx.x%)
Week 6					
n	XX	XX	XX	XX	XX
Yes	xx (xx.x%)	xx (xx.x%)	xx (xx.x%)	xx (xx.x%)	xx (xx.x%)
No	xx (xx.x%)	xx (xx.x%)	xx (xx.x%)	xx (xx.x%)	xx (xx.x%)

Continue for Weeks 8, 10, 12

Repeat for Loss or Change in Taste, Nausea, Vomiting, Diarrhea, Muscle Spasms or Cramps, Changes of Quality or Quantity of Hair in Treated Areas, Change in Frequency of Shaving, Other Systemic Sign or Symptoms, Other

Table 14.3.2.1.1: Summary of Treatment-Emergent Adverse Event Characteristics (Safety Population)
(Page 1 of 2)

	Patidegib Gel 2% QD (N=xx)	Patidegib Gel 2% BID (N=xx)	Patidegib Gel 4% QD (N=xx)	Patidegib Gel 4% BID (N=xx)	Vehicle Gel (N=xx)

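### For a primary safety objective, no table counts subjects by worst dermal grade, and the SAP text on laboratory results leaves out Week 6

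*SAP*

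**What the plan says.** The first primary objective in SAP section 3 is "The safety and tolerability of treatment with patidegib gel 2% or 4% or vehicle applied once or twice daily for 12 weeks".

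- **Dermal grades.** SAP 6.8.4.1 states that their frequency "will be summarized by treatment group and visit. All dermal safety and tolerability results will be listed". The shell, "Table 14.3.1.2.1: Summary of Dermal Safety and Tolerability (Safety Population"), gives grade counts at Baseline and Weeks 2, 6, 8, 10 and 12. The count row is "Number of tumors".
- **Recall period.** The shell's note reads "Local safety and tolerability is reported by the subject as the greatest intensity since the last visit or within 24 hours at Baseline". Protocol 9.3.1 applies that recall only to pain/burning and pruritus. Erythema, edema and scabbing/crusting are scored by the Investigator.
- **Systemic symptoms.** SAP 6.8.4.2: "Systemic symptoms will be summarized by treatment group and visit". The shell is yes/no.
- **Laboratory.** SAP 6.8.3: "Laboratory test results will be summarized with descriptive statistics at Baseline and Week 12"; the shifts in the same paragraph also run only from Baseline to Week 12. Protocol 10.8.3 calls for shift tables on "laboratory test results collected at Screening and Weeks 6, and 12". SAP Tables 14.3.3.1 and 14.3.3.5 show Week 6 and then continue to Week 12.
- **Windows.** SAP 6.1.3 maps early-termination and unscheduled data to visit windows. It excludes what falls outside them, and what maps to a visit with no planned analysis of that assessment.

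**The concern.** A safety objective asks how many subjects on each regimen ever had a notable finding. A sequence of per-visit tables does not answer that, because the reader cannot tell whether the same subject or a different one is counted each time. Counting tumors adds a second ambiguity, since a subject may treat one or two. The window rule adds a third: a visit made at the moment of stopping, often the most informative one for tolerability, can fall outside every column.

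For the laboratory data the issue is a contradiction about the only scheduled mid-treatment sample. Protocol 6.6 names abnormal liver function tests in the stopping criteria, so the planned tables should be clear on whether Week 6 is summarized. SAP section 8, which lists changes from the protocol, does not mention removing it.

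**Working it through.** Neither document gives a precision or sample-size figure for safety. The one figure that can be reproduced is the enrollment: 4 cohorts × (6 active + 3 vehicle) = 36, as stated. The vehicle groups are pooled (SAP 6.1), 4 × 3 = 12.

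**1. Unit of counting.** With one or two tumors each, six subjects contribute 6 to 12 tumors. Two severe tumors at a visit may belong to one subject (1/6 = 16.7%) or to two (2/6 = 33.3%). Even the single-visit subject count cannot be read.

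**2. Accumulation over visits.** Assume, for illustration, one tumor per subject, everyone assessed, and one severe subject at each of the five post-baseline visits.

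| Group | Shown at each visit | Fewest ever severe | Most ever severe |
|---|---|---|---|
| One regimen, n = 6 | 1/6 = 16.7% | 1/6 = 16.7% | 5/6 = 83.3% |
| Pooled vehicle, n = 12 | 1/12 = 8.3% | 1/12 = 8.3% | 5/12 = 41.7% |

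The minimum is the same subject every time; the maximum is a different subject every time. In terms of rates (assumed, not in the documents), a per-visit rate p gives an ever-affected rate of p if the subjects are always the same, and 1 − (1 − p)^5 if visits are independent:

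- p = 5%: 5% to 22.6%
- p = 10%: 10% to 41.0%
- p = 20%: 20% to 67.2%

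**3. Windows.** Before the Week 12 window opens on Day 82, the windows are Days 13–17, 40–46, 54–60 and 68–74: 5 + 7 + 7 + 7 = 26 of Days 1–81. An early-termination visit on Day 25 falls in none of them, so its dermal grades enter no column. Scheduled visits keep their nominal label and are not affected.

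**4. The adverse-event route.** Under Protocol 9.3.1 a local reaction must be reported as an adverse event if it needs concomitant therapy or causes interruption or discontinuation. A grade 3 score without such action need not be. The scales also differ: grade 3 erythema describes color and intensity (Protocol 9.3.1), whereas a severe adverse event is defined by limitation of activity and need for intervention (Protocol 9.3.5.4). A grade 3 reaction can therefore be a non-severe adverse event, or none.

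**5. Laboratory, text against shells.** Take a subject with an abnormal scheduled Week 6 result who stops on Day 60.

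- Under the 6.8.3 text, Week 6 is not summarized. The Day 60 sample maps to Week 8, where no laboratory analysis is planned, so it is excluded. The subject is in no shift table.
- Under Table 14.3.3.5, the Week 6 shift is counted.

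Even with the shells, one abnormal subject at each of Weeks 6 and 12 fits 1 to 2 of 6 subjects ever abnormal (16.7% to 33.3%), because there is no worst-value shift.

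**The case against.** The strongest reply is that adverse-event tables already do most of this work. Table 14.3.2.1.1 counts each subject once at maximum severity, and Table 14.3.2.1.3 does so by system organ class and preferred term. Reactions that led to therapy, interruption or discontinuation feed them, as do laboratory results the Investigator judges clinically significant (Protocol 9.3.3) and any incidence of the queried systemic symptoms (Protocol 9.3.5.2). This stands. A reader might infer that no table shows how many subjects ever had a severe finding, or that new class symptoms cannot be counted. The documents support neither. Nor does severe apply to the systemic tables (yes/no) or the laboratory shifts (below, within or above normal).

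Three further replies carry part of their weight:

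- **The protocol itself asks for by-visit dermal summaries, and the SAP adds listings by subject, tumor and visit.** True, and with about 36 subjects the worst grade could be derived by hand. That is still not a pre-specified summary of a primary objective.
- **The visit column keeps the reaction of a subject who stops.** This holds for scheduled visits, but fails for early-termination or unscheduled visits outside the windows.
- **The shells keep Week 6.** They do, so calling this a planned loss of data would go too far. It is a conflict within the SAP whose consequence depends on which part is followed.

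It would also be too strong to call all dermal scores snapshots, since pain/burning and pruritus cover the time since the last visit.

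**Conclusion.** The point holds in two limited parts.

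**Dermal.** No planned table gives subjects by worst post-baseline grade. What is missing is the subject-level count on the dermal scale. It matters most for grade 3 scores that triggered no adverse event, and for grades recorded at early-termination or unscheduled visits outside the windows. The ambiguity can be as wide as 1 to 5 of 6 subjects for an identical display. That range rests on the assumptions of one tumor per subject, complete assessment and one severe subject per visit. If every column shows zero, the count is zero for the data included and nothing is lost.

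**Laboratory.** SAP 6.8.3 contradicts Protocol 10.8.3 and the SAP's own shells on Week 6, and no table shows the worst on-treatment shift. A subject with an abnormal Week 6 result who leaves before the Week 12 window is missing from the shift tables only if the text prevails over the shells.

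Neither part undermines the collected data or the adverse-event analysis. Both are worth correcting because they bear on a primary objective.

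**What to change.** 1. Add to SAP 6.8.4.1 a table of subjects by worst post-baseline grade for each dermal sign. Take the maximum over tumors and over all post-baseline visits, and state that early-termination and unscheduled visits count even outside the 6.1.3 windows.
2. Correct SAP 6.8.3 to Weeks 6 and 12, in line with the protocol and Tables 14.3.3.1 and 14.3.3.5. Add a shift from Baseline to the worst on-treatment value that uses all on-treatment results, again regardless of window.

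While the shell is open, the note to Table 14.3.1.2.1 should be reconciled with Protocol 9.3.1 on which signs are subject-reported. An all-patidegib column is optional, since the four active groups do not overlap and subject counts can be added across them. A separate any-time systemic-symptom table would largely repeat the adverse-event tables.

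The cost is a few extra tables and some SAP wording. No new data are needed.
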